Given the serious personal consequences associated with trichotillomania and skin picking disorder, and the likelihood of success of dronabinol in treating both disorders, the aim of the present study was to examine the efficacy and safety of dronabinol vs placebo in adults with trichotillomania or skin picking disorder using a double-blind, placebo-controlled design.

We hypothesize that dronabinol will be more effective than placebo in reducing the frequency of hair pulling and skin picking and in improving overall psychosocial functioning after 10 weeks of treatment when compared to baseline.

Primary Aim/Objective

The aim of the present study is to examine the efficacy and safety of dronabinol vs placebo in adults with trichotillomania and skin picking disorder.

Co-Primary Endpoint(s):

The co-primary efficacy measures will be the change in hair pulling or skin picking frequency and urges to pull hair or pick skin for the past week as indicated by change in total score on the *NIMH Trichotillomania Symptom Severity Scale* (for TTM) or *Skin Picking Symptom Assessment Scale* (for SPD), reliable and valid clinician-administered measures (18-19), as well as the same scale modified for skin picking disorder, and the change in psychosocial functioning over the same time period using the *Sheehan Disability Scale* (20). The co-primary efficacy end points will be the change in these measures from baseline to week 10.

Secondary Aim/Objective

A secondary aim of the study is to examine the effects of dronabinol vs placebo on self-report measures of hair pulling, skin picking, quality of life, and measures of mood and anxiety.

Secondary Endpoint(s):

Secondary efficacy measures include the change in number of days per week pulling, the *Clinical Global Impressions–Improvement Scale* (CGI-I) rated global improvement of symptoms over time (results will be dichotomized as improved [CGI-I ratings of 1 or 2 very much/much improved] or not improved [CGI-I ratings of 3-7]) (20), the self-report *Massachusetts General Hospital Hairpulling Scale* (22), the *Skin Picking Symptom Assessment Scale*, the *Quality of Life Inventory* (23), the *Hamilton Depression Rating Scale* (24), the *Hamilton Anxiety Rating Scale* (25), and the *Tridimensional Personality Questionnaire*

Methodology

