- 8) Cognitive impairment that interferes with the capacity to understand and self-administer medication or provide written informed consent

Baseline Assessments:

Those subjects who appear appropriate for the study, based on telephone screening, will be invited for a baseline assessment. The duration of the baseline assessment will be approximately 90 minutes and will include the following: informed consent, demographic data, concomitant medications (no psychotropic medications will be allowed), and family history data. There will also be a physical examination (including weight, and vital signs, urine pregnancy test for women of childbearing years and urine drug screen, as well as a baseline blood draw to assess nutritional status. The blood draw is optional to the subject and will administered at the PI's discretion). Finally, the subjects will undergo a psychiatric evaluation (using the MINI International Neuropsychiatric Interview).

In addition, the following instruments will be completed at the screening visit: 1) NIMH Trichotillomania Symptom Severity Scale (or the same scale modified for skin picking); 2) Sheehan Disability Scale; 3) Massachusetts General Hospital Hairpulling Scale; 4) the 17-item

Hamilton Rating Scale for Depression (HAM-D); 5) the 17-item Hamilton Rating Scale for Anxiety (HAM-A); 6) Clinical Global Impression (Improvement and Severity) scale; 7) Cambridge Caffeine Use Questionnaire; 8) The Dietary Fat and Free Sugar Questionnaire and 9) the Quality of Life Inventory; 10) Cambridge-Chicago Trait Scale (12); the Skin Picking Symptom Assessment Scale (SP-SAS); and the Body Focused Repetitive Behavior Broad Assessment Measure (BFRB-BAM), a new scale being added for validation purposes. In addition, subjects will undergo cognitive assessments at baseline and study endpoint.

Cognitive Assessments: Assessments of cognitive control will be comprised of several valid paradigms (See below). These tasks are designed to probe dissociable neural circuitry and cognitive processes likely to be implicated in the pathophysiology of addictions. Task order was chosen arbitrarily and will be applied consistently across subjects, to minimize possible confounding factors of differences in task order across participants.

The following tasks will be administered at baseline and final visits:

- Stop Signal Task of Inhibitory Control (SST)
- Intra-dimensional/Extra-dimensional Set Shift Task (ID/ED task)
- One Touch Stockings Task (OTS)

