The primary analysis of efficacy for continuous measures will be analysis of variance (ANOVA), with terms for treatment to assess differences between treatment groups in the change from first randomization visit to endpoint using the last observation carried forward. The primary analysis for global improvement and response categories will be the Cochran-Mantel-Haenszel test using the last observation carried forward. The primary analysis for $\geq 5\%$ reduction in weight will be Fisher's exact test using the last observation carried forward.

Secondary endpoints analyses

Secondary outcome measures will include the change from first randomization visit to study endpoint in CGI severity and improvement scales, self-reported hair pulling behavior using the MGH-HPS, self-reported skin picking behavior using the SP-SAS, the change in depressive and anxiety symptoms, change in quality of life, and impacts on personality markers. We will use a longitudinal analysis comparing the rate of change of the outcome during the treatment period between groups. The difference in rate of change will be estimated by random regression methods. The model for the mean of the outcome will include terms for treatment, time, and treatment-by-time interaction. To account for the correlation of observations within participants, we will use SAS procedure MIXED with a first-order antedependence covariance structure. The longitudinal analyses will use all available observations from all time points from all participants who completed a randomization visit evaluation.

Safety analyses

We will evaluate differences between groups in the incidence of treatment-emergent adverse events using Fisher's exact test. Descriptive statistics will be used to evaluate changes in laboratory values, blood pressure and heart rate.

Sample Size

The sample size was calculated for the co-primary endpoint of change from randomization. For 80% power to compare the change from randomization, assuming a true effect size of 0.5 between treatment group and the placebo group, 50 participants with a BFRB will be needed in each treatment group based on a 2-group t test at the .05 level of significance. Given the low rates of adverse events expected with dronabinol, we expect few drop-outs from the study and therefore a smaller sample is needed.

Data Management Plan

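### CGI-Improvement is already a rating of change, but the secondary analysis takes its change from the randomization visit and compares slopes; this is not meaningful for the scale and conflicts with the planned responder test

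*Combined protocol and SAP*

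**What the plan says.** Four places in the combined protocol and SAP bear on CGI-I.

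- **Secondary Endpoint(s).** CGI-I is a secondary measure, described as "rated global improvement of symptoms over time (results will be dichotomized as improved" for ratings 1 or 2, and not improved for ratings 3 to 7.
- **Baseline Assessments.** The screening-visit instruments include the "Clinical Global Impression (Improvement and Severity) scale". Nothing says what an improvement rating means before treatment, or what value to enter.
- **Primary endpoint analysis.** "The primary analysis for global improvement and response categories will be the Cochran-Mantel-Haenszel test", with the last observation carried forward (LOCF).
- **Secondary endpoints analyses.** The outcomes include "change from first randomization visit to study endpoint in CGI severity and improvement scales". The method follows: "We will use a longitudinal analysis comparing the rate of change of the outcome during the treatment period between groups". Also: "The model for the mean of the outcome will include terms for treatment, time, and treatment-by-time interaction". The covariance is specified as "we will use SAS procedure MIXED with a first-order antedependence covariance structure", and the data are "all available observations from all time points from all participants who completed a randomization visit evaluation". CGI-I is not excepted.

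**The concern.** CGI-Severity rates the patient's state at a visit, so its change from baseline is well defined. CGI-I rates how far the patient has moved since the start, so the comparison with baseline is inside every rating. Subtracting a baseline CGI-I value takes a change of a change, and before treatment there is no improvement to rate. A slope fitted to CGI-I describes how fast the improvement rating is still moving. It does not describe how much improvement there is. Patients who improve early and stay improved contribute a flat stretch.

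The plan also offers a second and different analysis of the same scale, the responder comparison. The two can disagree. With no statement of which governs, the reported CGI-I result could be chosen after the data are seen.

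**Working it through.** The plan gives no figure for CGI-I, so there is nothing of its own to reproduce. The check is what the planned slope contrast returns for simple courses.

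**Inputs**

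- Visit times: weeks 0, 2, 4, 7 and 10. Methodology gives two visits at two-week spacing and then three-week spacing to week 10. Following-Up Visit Assessments confirms four follow-up visits.
- Responder rule: ratings 1-2 against 3-7 (Secondary Endpoint(s)).
- Assumption: a rating of 4 means no change, and 4 is what would be entered at baseline if anything is. The documents do not say.
- Assumption: the courses below are illustrative. The documents give no data on time to onset.

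**Formula.** Least-squares slope = Σ(t − t̄)y / Σ(t − t̄)².

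- With a baseline row: t̄ = 23/5 = 4.6, and Σ(t − t̄)² = 21.16 + 6.76 + 0.36 + 5.76 + 29.16 = 63.2.
- Weeks 2 to 10 only: t̄ = 23/4 = 5.75, and Σ(t − t̄)² = 14.0625 + 3.0625 + 1.5625 + 18.0625 = 36.75.

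The deviations sum to zero, so any constant may be removed from y. Taking off 2:

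- (4,2,2,2,2): 2(−4.6) = −9.2
- (4,4,3,3,2): 2(−4.6) + 2(−2.6) + 1(−0.6) + 1(2.4) = −12.6
- (4,3,3,2), weeks 2 to 10: 2(−3.75) + 1(−1.75) + 1(1.25) = −8.0

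| Course | Ratings, weeks 0, 2, 4, 7, 10 | Slope/week, weeks 2-10 | Slope/week, baseline 4 included | Week-10 status |
|---|---|---|---|---|
| Early, sustained | 4,2,2,2,2 | 0 | −9.2/63.2 = −0.146 | improved |
| Slower | 4,4,3,3,2 | −8.0/36.75 = −0.218 | −12.6/63.2 = −0.199 | improved |
| No response | 4,4,4,4,4 | 0 | 0 | not improved |

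**Without a baseline row.** If one arm followed the first course and the other the third, the treatment-by-time contrast would be 0 although one arm is all responders and the other has none. The model's treatment term would carry the gap, 2 − 4 = −2.

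**With a baseline row of 4.** The early responder is separated from the non-responder (−0.146 against 0, or about −1.46 over ten weeks). It still looks worse than the slower responder by 3.4/63.2 = 0.054 per week, although both finish at 2.

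**Weighting.** Generalised least squares with a special case of first-order antedependence (equal variances, adjacent correlation 0.5 or 0.8, both assumed) gives −0.162 and −0.164 for the early course, against −0.198 and −0.195 for the slower one. The ordering does not depend on the unweighted fit.

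**The responder rule.** At week 10 the first two courses count as the same success and the third as a failure.

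**The case against.** The case on the other side is substantial, and much of it stands.

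- **A sound analysis is already in the plan.** The dichotomised endpoint and the Cochran-Mantel-Haenszel test fit each other. A reader might count three conflicting treatments of CGI-I. The documents support two: the responder comparison, and the change and slope analysis.
- **A reader might infer that the plan would miss a sustained response altogether.** It would not. A zero slope arises only if no baseline CGI-I row enters the model, and the scale is listed at screening. Even then the treatment term shows the difference. What remains is that the contrast the plan names, the difference in rate of change, would be zero. A rating of 2 is also much improved on the plan's own wording, not a complete response.
- **The early-versus-late example is not peculiar to CGI-I.** The same numbers on CGI-Severity would give the same slopes, because this is a property of any linear-slope comparison. What is peculiar to CGI-I is that it has no meaningful baseline, so the slope depends on an undefined entry.
- **A reader might infer that CGI-I has been promoted to a primary endpoint.** The word primary in that paragraph names the main method for a type of outcome; it is used in the same way for a weight-reduction category. Secondary Endpoint(s) keeps CGI-I secondary. The label still sits under Primary endpoint analysis and should be cleared up.

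One could argue that the label already makes the responder test govern. The plan does not say so, and the next section applies the slope model without exception.

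**Conclusion.** The point holds as a specification error in one secondary analysis. By its wording, the plan analyses CGI-I as change from the randomization visit with a rate-of-change model. That is wrong for a scale whose ratings are already changes, and it conflicts with the plan's own responder analysis.

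In the worked courses, the slope contrast is 0 between sustained responders and non-responders when only post-baseline ratings are used. It ranks a slower response ahead of an early one by 0.054 points per week when a baseline of 4 is assumed. These figures rest on the invented courses and on reading 4 as no change. The effect in the trial cannot be sized from the documents, because they give neither onset patterns nor a rule for the baseline entry.

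The co-primary analyses do not use CGI-I and are unaffected. The change is worth making because it is cheap and removes a choice between two results.

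**What to change.** In Statistical Analysis:

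1. Under Secondary endpoints analyses, limit the change and rate-of-change analysis to CGI-Severity and take CGI-I out of that list.
2. State that CGI-I is analysed once, as the proportion rated 1-2 against 3-7 at endpoint, with the Cochran-Mantel-Haenszel test and the LOCF rule already planned. Keeping that rule matters: specifying week-10 responders alone would leave missing ratings without any rule.
3. Label this analysis secondary, and move or reword the sentence that now stands under Primary endpoint analysis.
4. State that any CGI-I entry made at the baseline visit is not used in the analysis. The assessment list can then stay as it is.

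The cost is a few sentences. No data, visits or methods are added. Because the analysis plan is part of the protocol, the edit would go to the IRB as an amendment, and it should be made before unblinding.

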- Rapid Visual Processing Task (RVP)
- Spatial Working Memory Task (SWM)
- Cambridge Gambling Task (CGT)

Following-Up Visit Assessments

All follow-up visits will include all psychiatric measures (except the MINI which will be done at baseline only) and safety measures (adverse events, vital signs, C-SSRS). There will be four follow up visits for a total of five visits.

Subject Compensation

Subjects will be compensated \$20 per visit, for a total of \$100. Compensation will be given in the form of a check at the end of the study, as per University of Chicago protocol.

Safety Assessments

Safety and tolerability will be assessed using spontaneously reported adverse events data, Columbia–Suicide Severity Rating Scale (C-SSRS), vital signs, and by evaluating premature termination. Safety assessments (C-SSRS, sitting blood pressure, heart rate, adverse effects, and concomitant medications) will be documented at each visit. Subjects who are an immediate suicide risk will be removed from the study and appropriate clinical intervention (e.g. hospitalization) will be arranged. Urine pregnancy tests will be performed at the initial visit. Subjects who have a positive urine pregnancy test will be excluded from the study. Assessment of side effects will be done at each visit. AEs will be coded by system organ class (SOC) and preferred term (PT) using the Medical Dictionary for Regulatory Activities (Med- DRA) Version 11.1. The incidences of all AEs will be summarized descriptively. In terms of vital signs, those subjects with abnormal blood pressures will be assessed for symptoms of hypo- or hypertension. Asymptomatic subjects will be evaluated each visit for changes in vital signs. In the case of hypertensive emergencies (BP greater than 210/120), appropriate referral to the emergency room will be made. In the case of hypotension (BP less than 90/60), participants will be evaluated for symptoms of hypotension and if symptomatic, appropriate interventions will be made.

Seizure and seizure-like activity have been reported in patients receiving dronabinol. Therefore, history of seizures will be an exclusion criterion. If a seizure occurs, dronabinol will be discontinued. Participants will be advised to discontinue dronabinol and contact a healthcare provider immediately if they experience a seizure.

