- Any moderate adverse event which appears definitely, probably, or possibly related to study participation will be reported to the University of Chicago IRB in writing within 20 working days.
- Any mild adverse event will be summarized in the IRB annual progress reports.

Statistical Analysis

Design/Randomization

The study is a double-blind, placebo-controlled study. Participants will be randomized (1:1) to receive dronabinol or placebo by the University of Chicago Investigational pharmacy in block sizes of eight, using computer-generated randomization with no clinical information.

Due to the pandemic of COVID19, study participants can perform their baseline and follow-up visits online using encrypted Zoom instead of in person visits. All inventories will be assessed. Blood samples and urine toxicology, however, will be at the discretion of the study PI. In cases where they are considered medically necessary, the participant can have them drawn locally and submitted to the study team.

Efficacy Analysis

For statistical analysis, the full-analysis set will be defined as all participants who took at least 1 dose of the study drug and had at least 1 post-randomization primary efficacy assessment. The safety-analysis set will be defined as all randomized participants who took at least 1 dose of the study drug and completed at least 1 post-randomization safety assessment. Participants with trichotillomania and skin picking disorder will be grouped as one BFRB group.

We will compare the baseline characteristics of both groups using Fisher's exact test for categorical variables and the t test for continuous variables. We will calculate adherence to treatment, based on the number of pills returned at each visit, as the number of pills taken divided by the number of days in the study $\times 100\%$.

Primary endpoint analysis

The primary outcome measure will be the change from first randomization visit to study endpoint in total composite score on the NIMH Trichotillomania Symptom Severity Scale(s) and the Sheehan Disability Scale.

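### MGH-HPS and SP-SAS are modelled in all participants whatever their diagnosis, so the hair-pulling and skin-picking estimates are likely to be diluted by people without the behaviour

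*Combined protocol and SAP*

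**What the plan says.** Either diagnosis is enough to enrol (Subjects, inclusion criteria), and having both is not an exclusion. Efficacy Analysis then pools them: "Participants with trichotillomania and skin picking disorder will be grouped as one BFRB group".

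Secondary endpoints analyses names among its outcomes "self-reported hair pulling behavior using the MGH-HPS, self-reported skin picking behavior using the SP-SAS". On the model it says: "The model for the mean of the outcome will include terms for treatment, time, and treatment-by-time interaction". On the population it says: "The longitudinal analyses will use all available observations from all time points from all participants who completed a randomization visit evaluation". There is no diagnosis term and no subset for either scale.

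On collection, Baseline Assessments says that "the following instruments will be completed at the screening visit" and lists MGH-HPS and SP-SAS without a condition. In the same list the NIMH scale does have an alternative form for skin picking. Following-Up Visit Assessments says: "All follow-up visits will include all psychiatric measures (except the MINI which will be done at baseline only". The COVID-19 paragraph under Design/Randomization keeps every inventory for online visits.

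Secondary Endpoint(s) also includes "the change in number of days per week pulling", but Secondary endpoints analyses does not list it. No section gives the expected split between the diagnoses, the score ranges, or the way a scale is recorded for someone without the behaviour.

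**The concern.** The secondary aim asks what dronabinol does to self-reported hair pulling and to self-reported skin picking. A participant who only picks skin has little or no hair pulling to reduce, and the reverse holds for SP-SAS. If such people complete the scale, their near-zero changes are averaged in with those of people who have the behaviour. The estimate then depends on how many participants happen to show the behaviour as well as on the drug, and it cannot be read as the effect on hair pulling among people who pull, or on picking among people who pick. A small value could mean a weak drug or a small share of affected participants.

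**Working it through.** **The plan's own figure.** The plan gives no effect size, case mix or sample size for these scales. Its one related figure, 50 per group for the co-primary endpoint at 0.5 SD and 80% power, reproduces at a one-sided 0.05 level: 2 × (1.645 + 0.842)² / 0.5² = 49.5, so 50. A two-sided level gives 63. That figure does not bear on this point.

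**Inputs.**
- From the documents: 50 participants randomised 1:1 (Methodology), so 25 per arm; visits at weeks 0, 2, 4, 7 and 10 (from the visit intervals in Methodology).
- Borrowed as an illustration: an effect of 0.5 SD in those affected (Sample Size, stated there for the co-primary endpoint).
- Assumed: share p showing the behaviour of 0.25, 0.50 or 0.75; mean placebo change in those affected of 0 or 1 SD; everyone else at floor with zero change.

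**Formulas.** Let the change among those affected have SD 1 and arm mean m, where m in the dronabinol arm is the placebo value plus 0.5.
- Raw difference between arms = p × 0.5.
- Variance of change in an arm = p + p(1 − p)m². The second term is the noise from mixing people with and without the behaviour.
- Standardised effect = 0.5p / √(mean of the two arm variances).

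**Worked case, p = 0.50.** The raw difference is 0.25.
- Placebo change 0: arm variances 0.500 and 0.5625, mean 0.531, SD 0.729, standardised effect 0.25 / 0.729 = 0.343.
- Placebo change 1 SD: arm variances 0.750 and 1.0625, mean 0.906, SD 0.952, standardised effect 0.25 / 0.952 = 0.263.

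**All cases.** Power is two-sided at 0.05, from the noncentral t for a simple two-group comparison of change. The restricted analysis has an expected 25p per arm and an effect of 0.5. Paired entries are for placebo change 0, then 1 SD.

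| p | Raw difference | Standardised effect, pooled | Power, pooled | Power, restricted (n per arm) |
|---|---|---|---|---|
| 0.25 | 0.125 | 0.239; 0.168 | 13.2%; 9.0% | 12.7% (6.25) |
| 0.50 | 0.250 | 0.343; 0.263 | 22.1%; 14.9% | 22.4% (12.5) |
| 0.75 | 0.375 | 0.426; 0.365 | 31.5%; 24.4% | 31.9% (18.75) |

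The raw effect shrinks exactly in proportion to p. The standardised effect keeps 0.48, 0.69 and 0.85 of its value with no placebo change, and 0.34, 0.53 and 0.73 with a placebo change of 1 SD. It therefore shrinks less than proportionally or about proportionally.

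**Check on slopes.** In 20,000 simulated trials per value of p, with 25 per arm at the five visits and a true slope difference of −0.05 per week among those affected, the mean estimates were −0.01241, −0.02497 and −0.03743. These are 0.248, 0.499 and 0.749 of the true value. The simulation used least-squares slopes per participant rather than the planned antedependence model.

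**Both scales together.** If nobody showed both behaviours, the two shares could sum to at most 1, so at least one scale would keep no more than half of its effect.

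**The case against.** The strongest reply is that the plan never says a non-applicable scale is scored at floor. The sentence about all available observations can be read as a missing-data rule, in contrast to the last observation carried forward used for the primary analysis. If a skin-picking participant's MGH-HPS is left blank, that person contributes nothing and there is no dilution. The authors also match scales to diagnosis elsewhere: the NIMH scale has a skin-picking form, and Co-Primary Endpoint(s) ties SP-SAS to skin picking disorder. This stands to the extent that floor entry is an inference. But the collection text points to completion by everyone, and the secondary use of the two scales carries no such matching. If blanks were intended, the analysis population for each scale would still be unstated.

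A second reply is that the pooled average is not biased for the pooled population the protocol chose. That is correct. It is a poor answer to a secondary aim about hair pulling and skin picking, but calling it biased presumes a diagnosis-specific target.

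A reader might also infer three stronger things that the documents do not support:
- *The shrinkage depends only on recruitment mix.* Participants may have both disorders or subthreshold behaviour, so p is the share showing the behaviour, not the share enrolled under that diagnosis.
- *The mixture breaks the model's variance assumptions.* The antedependence structure lets variances differ by visit, and randomisation gives both arms the same expected mixture. In the worked case with a placebo change of 1 SD, the arm variances are 0.75 and 1.06, a modest difference with equal arms.
- *Weekly days of pulling are analysed in everyone by this rule.* That measure is missing from the list the rule governs, so its analysis is unspecified.

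**Conclusion.** The point holds for MGH-HPS and SP-SAS as secondary outcomes. Followed as written, the plan collects both scales from all participants and models them in the pooled group without regard to diagnosis. If participants without the behaviour complete the scale and barely change, the raw treatment-by-time estimate is about p times the effect in those affected. The size in this trial cannot be fixed, because p is not documented.

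It would be wrong to conclude that the trial loses much power through this rule or that its main result is at risk. In the scenarios above, pooled power runs from about equal to the restricted analysis to 7.5 percentage points below it (14.9% against 22.4%, and 24.4% against 31.9%). The co-primary symptom scales are matched to diagnosis, and the remaining secondary scales that apply to everyone are not touched. What suffers is the interpretation of two secondary estimates in a study that describes itself as a pilot. This is a worthwhile, inexpensive improvement.

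**What to change.** Before unblinding, amend Secondary endpoints analyses to state that:
- MGH-HPS is analysed in participants with current trichotillomania at baseline, and SP-SAS in those with current skin picking disorder at baseline; participants with both count in both.
- Weekly days of pulling is a listed outcome, analysed in the trichotillomania subset.
- The number per arm is reported for each of these analyses, and the way a non-applicable scale is recorded is specified.
- The pooled group is kept for scales that apply to everyone (CGI, mood, anxiety, quality of life).

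The cost is a change of wording and a smaller n per scale. Any subthreshold pulling or picking in the excluded participants is not used, so some information may be given up. Fixing the subsets before unblinding prevents the population from being chosen after the results are seen.
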